9.1.2.2. Percentage of Body Surface Area

The blinded assessor will evaluate the percentage involvement of psoriasis on each patient's BSA on a continuous scale from 0% (no involvement) to 100% (full involvement), in which 1% corresponds to the size of the patient's hand (including the palm, fingers, and thumb) (National Psoriasis Foundation [NPF] 2009).

9.1.2.3. American College of Rheumatology 20 Responder Index

ACR20 response is a secondary efficacy measure for which a patient must satisfy the following:

- 1) \geq 20% improvement from baseline in tender joint count (TJC) and
- 2) ≥20% improvement from baseline in swollen joint count (SJC) and
- 3) ≥20% improvement from baseline in at least 3 of the following 5 ACR Core Set criteria:
 - a. Patient's Assessment of Pain VAS
 - b. PatGA VAS
 - c. PGA VAS
 - d. patient's assessment of physical function as measured by the HAQ-DI
 - e. acute-phase reactant as measured by high sensitivity (assay) CRP (hs-CRP)

9.1.2.3.1. American College of Rheumatology Core Set

a. Tender Joint Count

TJC joint assessments will be performed by a blinded assessor.

For ACR measures, the number of tender and painful joints will be determined by examination of 68 joints (34 joints on each side of the patient's body). Any joints that require intra-articular injections during the study (according to Section 7.7) should be excluded from evaluation from the time of the injection to the conclusion of the study.

Joints will be assessed for tenderness by pressure and joint manipulation on physical examination. The patient will be asked for pain sensations on these manipulations and watched for spontaneous pain reactions. Any positive response on pressure, movement, or both will then be translated into a single tender-versus-nontender dichotomy.

Missing, replaced, ankylosed, or arthrodesed joints will be identified by the investigator at the Screening Visit and will be excluded from evaluation during the trial.

b. Swollen Joint Count

SJC joint assessments will be performed by a blinded assessor.

For ACR measures, the number of swollen joints will be determined by examination of 66 joints (33 joints on each side of the patient's body). Any joints that require intra-articular injections during the study (according to Section 7.7) should be excluded from evaluation from the time of the injection to the conclusion of the study.

Joints will be classified as either swollen or not swollen. Swelling is defined as palpable fluctuating synovitis of the joint. Swelling secondary to osteoarthritis will be assessed as not swollen, unless there is unmistakable fluctuation. Dactylitis should be counted as 1 swollen joint.

Missing, replaced, ankylosed, or arthrodesed joints will be identified by the investigator at the Screening Visit and will be excluded from evaluation during the trial.

c. Patient's Assessment of Pain Visual Analog Scale

The patient will be asked to assess his or her current level of joint pain by marking a vertical tick on a 100-mm horizontal VAS where the left end represents no joint pain and the right end represents worst possible joint pain. The Patient's Assessment of Pain VAS should be administered *prior to* the TJC and SJC examinations.

Results will be expressed in millimeters measured between the left end of the scale and the crossing point of the vertical line of the tick; this procedure is applicable for all VAS used in the trial.

d. Patient's Global Assessment of Disease Activity Visual Analog Scale

The patient's overall assessment of his or her PsA activity will be recorded using the 100-mm horizontal VAS. Patients will be asked, "Considering all the ways your PsA has affected you, how do you feel your PsA is today?" where the left end represents "very well" and the right end represents "very poor."

e. Physician's Global Assessment of Disease Activity Visual Analog Scale

The investigator, who must be a physician, will be asked to give an overall assessment of the severity of the patient's current PsA activity using a 100-mm horizontal VAS, where 0 represents no disease activity and 100 represents extremely active disease.

f. Patient's Assessment of Physical Function as Assessed by the Health Assessment Questionnaire-Disability Index

The HAQ-DI is a patient-reported standardized questionnaire that is commonly used in PsA to measure disease-associated disability (assessment of physical function). It consists of 24 questions referring to 8 domains: dressing/grooming, arising, eating, walking, hygiene, reach, grip, and other daily activities (Fries et al. 1980; Fries et al. 1982).

The disability section of the questionnaire scores the patient's self-perception on the degree of difficulty (0 = without any difficulty, 1 = with some difficulty, 2 = with much difficulty, and 3 = unable to do), covering the 8 domains. The reported use of special aids or devices and/or the need for assistance of another person to perform these activities is also assessed. The scores for each of the functional domains will be averaged to calculate the functional disability index. An MCID is a clinically relevant change in a patient's status. The HAQ-DI MCID has been estimated to be about 0.35 for patients with PsA (Mease et al. 2011). Details of scoring and calculations are presented in the statistical analysis plan (SAP).

g. C-Reactive Protein

CRP will be the ACR Core Set measure of acute-phase reactant. It will be measured with a high sensitivity assay at the central laboratory to help assess the effect of ixekizumab on the patient's PsA.

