Nonopiod analgesics (paracetamol and acetaminophen)	Y	Y	Allowed up to the maximum recommended doses for pain. May be administered as needed basis during the study, but should be withheld within 24 hours of a visit. May be used at doses ≤1000 mg for premedication for allergic/hypersensitivity reactions from injections (see Section 7.8.3)
Topical steroids	Y	Y	Allowed as needed, but not within 24 hours of PASI assessment
Oral corticosteroids	Y	Y	Allowed doses: ≤ an average daily dose of 10 mg/day of prednisone or equivalent)
Intravascular and IM glucocorticoid	N	N	Not allowed
Intra-articular glucocorticoid	N	N	Allowed on a limited basis: it is recommended that there be no more than 1 injection (one injection = one large joint or up to 5 small joints or one soft tissue)
Inhaled steroids	Y	Y	As needed or regular use for asthma is permitted
Nasal corticosteroids	Y	Y	Use for allergies is permitted

Drug Class	As Needed	Chronic Use	Conditions for Use
Medicated shampoos			Allowed
Topical moisturizers/emollients and other nonprescription topical products	Y	Y	Topical moisturizers/emollients and other nonprescription topical products that do not contain, urea, >3% salicylic acid, alpha- or betahydroxyl acids, corticosteroids, or vitamin D3 analogs
Bath oils and oatmeal bath preparations			Allowed
oam preparations			These topical therapies are not to be used within 12 hours prior to a study visit

Abbreviations: BCG = Bacillus Calmette-Guérin; bDMARD = biological disease-modifying anti-rheumatic drugs; COX-2 = cyclooxygenase-2; csDMARD = conventional synthetic disease-modifying anti-rheumatic drugs; IM = intramuscular; JAK = Janus kinase; MTX = methotrexate; N = No; NSAID = nonsteroidal anti-inflammatory drug; PASI = Psoriasis Area and Severity Index; PDE4 = phosphodiesterase type 4; Y = Yes; WHO = World Health Organization.

Table RHCF.7.4. Allowed Concomitant Medications in the Post-Treatment Follow-Up Period (Period 3)

Drug Class	As Needed	Chronic Use	Conditions for Use
bDMARDs	Y	Y	Allowed Follow local guidance; at the discretion of investigator
PDE4 or JAK inhibitors	Y	Y	Allowed Follow local guidance; at the discretion of the investigator
csDMARDs	Y	Y	Allowed
Live vaccines (including BCG)	N	N	Not allowed
Phototherapy	Y	Y	Allowed
NSAIDs, COX-2 inhibitors	Y	Y	Allowed
Opiate analgesics	Y	Y	Allowed
Nonopiod analgesics (paracetamol and acetaminophen)	Y	Y	Allowed
Topical steroids	Y	Y	Allowed
Oral corticosteroids	Y	Y	Allowed

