6.4. Handling of Dropouts or Missing Data

6.4.1. Non-Responder Imputation (NRI) for Clinical Response

Analysis of categorical efficacy and health outcome variables will be based on treatment success/failure. This approach yields results numerically identical to non-responder imputation (NRI), but it is interpreted differently. Patients will be considered treatment failures (or non-responders) if they do not meet the clinical response criteria or have missing clinical response data at a particular time point of analysis.

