Appendix 3. Algorithm for Calculating Joint Counts

Joints are evaluated and recorded as either non-evaluable, or if evaluable, then if tenderness is present or absent, and if swelling is present or absent. In total, 68 joints are assessed for tenderness and 66 are assessed for swelling. Hips are not assessed for swelling.

The number of tender/swollen joints will be calculated by summing all joints checked to have tenderness/swelling present. If at least half but not all of the joints are evaluable, then the observed prorated joint count will be calculated instead. The prorated scores for TJC will be adjusted based upon the number of evaluable joints: the counted score will be multiplied by 68 then divided by the number of joints evaluated (excluding non-evaluable joints and any joints with a missing response). For example: if only 60 of the 68 joints are assessed to be evaluable at a visit, and 32 of those 60 are tender, the prorated joint count is $(32/60) \times 68 = 36.27$ (not 32). The prorated joint count will be rounded up to the next integer and be used in calculating the percent change from baseline in TJC. The same algorithm will be applied to the calculation of percent change from baseline in SJC with the exception that the counted score will be multiplied by 66 then divided by the number of joints evaluated. If less than half of the joints are evaluable, the number of tender/swollen joints is missing.

This same algorithm will be used for the calculation of TJC and SJC based on 28 joints, which is part of the 28 diarthrodial joint count, based on C-reactive protein (DAS28-CRP) score.

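### Injecting two or more active joints after Week 24 lowers the prorated joint count against an unchanged baseline, so the ACR joint criteria at Weeks 32 to 52 can be met without real improvement

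*Protocol*

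**What the plan says.** Protocol 9.1.2.3.1 gives one instruction for both counts: "Any joints that require intra-articular injections during the study (according to Section 7.7) should be excluded from evaluation from the time of the injection". The exclusion lasts until the study ends. Joints that could not be assessed from the start (replaced or ankylosed ones, for example) are identified at screening, so they are absent from baseline and follow-up alike.

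SAP 6.1.1 fixes baseline at the first dose, and SAP Appendix 2 measures percent improvement from it. No rule later removes an injected joint from the baseline count.

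SAP Appendix 3 prorates when some joints are not evaluable: "the counted score will be multiplied by 68 then divided by the number of joints evaluated", with 66 in place of 68 for swelling. Then: "The prorated joint count will be rounded up to the next integer and be used in calculating the percent change from baseline in TJC". SAP Table RHCF.6.3 shows the same scaling without rounding and refers to Appendix 3 for details.

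Protocol 7.7 does not allow intra-articular glucocorticoid up to Week 24 (Table RHCF.7.2). For Weeks 24 to 52 the text in Table RHCF.7.3 allows limited use and recommends at most one injection, with the definition "one injection = one large joint or up to 5 small joints" (or one soft tissue). The same row is marked No under both as-needed and chronic use.

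Under SAP 6.4.1 a patient is a nonresponder only "if they do not meet the clinical response criteria or have missing clinical response data at a particular time point of analysis". An injection does not enter that rule.

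**The concern.** Proration assumes that the joints left out resemble the joints still counted. Injected joints are left out because they needed treatment, so active joints are replaced by the average of the others. Baseline still holds every joint, and the difference reads as improvement.

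The counts feed ACR20/50/70, the combined ACR50 and PASI 100 response, PsARC, MDA, DAS28-CRP, mCPDAI and the change in each count. The 52-week time course of these measures is a stated secondary objective, and SAP Table RHCF.6.4 analyses time to first ACR response up to Week 52. Joint assessors are blinded (Protocol 7.3), but treatment is open-label, so injection use could differ by arm with knowledge of allocation. A blinded count cannot correct for joints that have been removed from it.

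**Working it through.** **The plan's own figure.** Appendix 3 gives this example: "if only 60 of the 68 joints are assessed to be evaluable at a visit, and 32 of those 60 are tender". 32/60 × 68 = 36.27, as stated; rounded up it is 37.

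**Formula.** Let T be 68 (tender) or 66 (swollen), B the baseline count, k the current active count, and j the number of those k joints that are injected. All T joints are otherwise evaluable.

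- Scored count = (k − j) × T/(T − j), rounded up
- Improvement = (B − scored count)/B

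**One injected joint.** (k − 1) × T/(T − 1) = (k − 1) + (k − 1)/(T − 1). For k from 2 to T the last term is above 0 and at most 1, so rounding up returns exactly k. Example: swollen count 10 to 6, one injected: 5 × 66/65 = 5.08, rounded to 6; improvement stays at 40%. Only the last active joint disappears (1 to 0). The only ACR cut-off this crosses is ACR70 at B = 3 (66.7% to 100%).

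**Two or more injected joints.** Proration adds back only j(k − j)/(T − j). While that is above 0 and at most 1, the rounded count falls by j − 1; if no other joint is active, it falls by j.

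| Count | B to k | j | Prorated | Rounded | Improvement before | After |
|---|---|---|---|---|---|---|
| Swollen | 6 to 4 | 2 | 2 × 66/64 = 2.06 | 3 | 33% | 50% |
| Swollen | 10 to 6 | 2 | 4 × 66/64 = 4.13 | 5 | 40% | 50% |
| Swollen | 8 to 6 | 5 | 1 × 66/61 = 1.08 | 2 | 25% | 75% |
| Swollen | 6 to 5 | 5 | 0 | 0 | 17% | 100% |
| Tender | 12 to 8 | 3 | 5 × 68/65 = 5.23 | 6 | 33% | 50% |
| Tender | 10 to 8 | 5 | 3 × 68/63 = 3.24 | 4 | 20% | 60% |

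The 8-to-6 row passes even the ACR70 cut-off for that count. The 6-to-5 row also meets the MDA swollen-joint item (at most 1).

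**How many combinations cross.** Taking every B of at least 3 (the entry minimum) and every k, these (B, k) pairs cross the ACR50 cut-off on one count:

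| j | 1 | 2 | 3 | 4 | 5 |
|---|---|---|---|---|---|
| Tender (T = 68) | 0 | 66 | 108 | 161 | 201 |
| Swollen (T = 66) | 0 | 64 | 106 | 155 | 195 |

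These show what is possible, not how often it happens.

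**Two ways a single joint can matter.**

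- Another joint was already non-evaluable. With 67 evaluable and 3 tender at baseline, 3 × 68/67 rounds up to 4. Two tender later gives 2 × 68/67, rounded up to 3 (25%). After one is injected, 1 × 68/66 rounds up to 2 (50%).
- The Table RHCF.6.3 formula is programmed without rounding. Tender count 5 to 3 with one injected gives 2 × 68/67 = 2.03, so improvement goes from 40% to 59%. Unrounded, 33 tender-count pairs cross the ACR50 cut-off with one injected joint.

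**The case against.** A reader might infer that injecting any one flaring joint creates an ACR response. The documents do not support that. With all joints evaluable, the Appendix 3 round-up leaves the count unchanged for every k of 2 or more, and no ACR20 or ACR50 cut-off is crossed. One large joint is among the permitted forms of injection. This part of the objection stands in full.

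Crossing one count is not a response: ACR50 also needs the other count and 3 of 5 further items. That stands too. But a joint that is both tender and swollen leaves both counts. If the tender 10-to-8 and swollen 8-to-6 rows describe one patient with the same 5 joints injected, both joint criteria are met (60% and 75%), and the 3 of 5 items decide.

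The larger examples need most of the active joints to be small and injected together, and the protocol recommends no more than one injection. However, that one injection may cover up to 5 small joints, and two are enough to cross.

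The affected results are secondary or exploratory and outside the multiplicity procedure. That limits the consequence; it does not make the count right. The SAP does not class an injection as treatment failure, and excluding injected joints is a possible convention. The difficulty here is that the exclusion applies to follow-up only.

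**Conclusion.** The concern holds for sessions in which two or more active joints are injected after Week 24. The tender or swollen criterion can then be met at Weeks 32, 40 and 52, and time to first response up to Week 52 can be affected, without real improvement. A single injected joint matters only if it was the last active joint, if other joints were already non-evaluable, or if the unrounded formula is used.

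A reader might also infer that the primary result is biased. The documents do not support that. Intra-articular steroid is not allowed up to Week 24, its anticipated use in that period is an exclusion criterion, excluded medication is an important protocol violation (SAP Table RHCF.6.9), and SAP 6.17 plans additional analyses of the primary and/or major secondary endpoints in patients without any, or a subset of, violations. Only deviations could reach the Week 24 endpoints.

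No effect on response rates or on the difference between arms can be computed, because the documents give neither the frequency of injection nor its split by arm. The worked figures assume that every injected joint was active when injected and, except where stated, that all other joints were evaluable.

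**What to change.** In SAP Appendix 3, score a joint that becomes non-evaluable because of an intra-articular injection as tender and swollen (where assessed) from the injection onward, and keep it in the 68, 66 or 28 denominator:

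(active evaluable joints + injected joints) × T/(evaluable joints + injected joints), rounded up.

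Reserve proration for joints non-evaluable since screening or missing for other reasons. The swollen 6-to-4 case then gives (2 + 2) × 66/(64 + 2) = 4, or 33%; the 8-to-6 case gives (1 + 5) × 66/(61 + 5) = 6, or 25%. Carrying forward the last visit's status would be weaker: visits after Week 24 are 8 to 12 weeks apart, so a joint that flared and was injected between visits would keep an inactive score. State in Table RHCF.6.3 that the count is rounded up.

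Identify the joints by matching newly non-evaluable joints to the concomitant-medication record. The documents do not say that this record names the joint, so the change in evaluability may have to carry most of the identification.

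The cost is one scoring rule and a derived flag. Response rates at Weeks 32 to 52 will be slightly lower in injected patients, and joints that the injection helped will be scored conservatively. Keeping the present exclusion rule as a sensitivity analysis shows how much that matters. The change concerns scoring only.

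Separately, the Week 24 to 52 intra-articular row of Table RHCF.7.3 contradicts itself (No in both use columns, limited use allowed in the text) and must be reconciled.

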9.1.2.4. American College of Rheumatology 50 and 70 Responder Index

ACR50 and ACR70 responses are secondary efficacy endpoints and are improvements of at least 50% and of at least 70%, respectively, in the multiple disease assessment ACR criteria. The ACR50 and ACR70 are calculated similarly to ACR20, as described in Section 9.1.2.3.

9.1.2.5. Individual Components of the American College of Rheumatology Core Set

The individual components of the ACR Core Set will be measured including TJC (68 joint count), SJC (66 joint count), Patient's Assessment of Pain VAS, PatGA VAS, PGA VAS, Patient's Assessment of Physical Function as measured by the HAQ-DI, and CRP (Section 9.1.2.3.1).

9.1.2.6. Psoriatic Arthritic Response Criteria

The PsARC is a composite criteria reported in terms of the percentage of patients achieving response according to the following criteria: PGA, PatGA, TJC, and SJC. Overall response is defined by improvement from the baseline assessment in 2 of the 4 criteria, 1 of which must be a joint count; there must not be worsening in any of the 4 criteria:

- 1. At least 30% reduction in TJC
- 2. At least 30% reduction in SJC
- 3. At least a 1 point reduction in physician's assessment
- 4. At least a 1 point reduction in patient's assessment

The PsARC response was modified in this study by using the PGA and the PatGA on a 100 mm VAS described in Section 9.1.2.3.1 instead of a 5-point Likert scale in the original criteria. The results from the 2 VAS measures were assessed as a difference from baseline (in mm), but criteria 3 and 4, above, were changed to "at least a 20 mm reduction" (Clegg 1996).

9.1.2.7. Minimal Disease Activity

The MDA score has been developed based on current expert opinion and uses a composite of 7 key outcome measures used in PsA to encompass all of the domains of the disease to measure

the overall state of a patient's disease (Coates et al. 2010a; Coates and Helliwell 2010b). The overall state of disease activity is deemed a useful target of treatment by both the patient and the physician, given current treatment possibilities and limitations. Preliminary validation work supports the use of the MDA criteria in both observational cohorts and in interventional trial cohorts. The PsA MDA criteria have evidence supporting their use within the OMERACT filter of truth, discrimination, and feasibility.

• MDA: Patients are classified as achieving MDA if they fulfill 5 of 7 outcome measures: TJC ≤1; SJC ≤1; psoriasis activity and severity index (PASI total score) ≤1 or BSA ≤3; patient pain VAS score of ≤15; patient global disease activity VAS score of ≤20; HAQ-DI score ≤0.5; and tender entheseal points ≤1.

9.1.2.8. Modified Composite Psoriatic Disease Activity Index

The Modified CPDAI is a validated instrument intended to assess composite psoriatic disease activity and response to therapy (Mumtaz et al. 2011). This instrument assesses individual domains involved as well as the global effect of disease in all dimensions by which each patient may be affected. Domains include peripheral arthritis as assessed by the number of tender and swollen joints and the HAQ-DI, skin as assessed by the PASI and the DLQI, enthesitis as assessed by the number of sites with enthesitis and the HAQ-DI, and dactylitis as assessed by the number of digits affected and the HAQ-DI. Scores range from 0 to 12, with a higher score indicating higher disease activity.

9.1.2.9. Leeds Enthesitis Index

If the patient has enthesitis, the LEI will be administered by a blinded assessor. The LEI has been developed specifically for use in PsA. It measures enthesitis at 6 sites (lateral epicondyle, left and right, medial femoral condyle, left and right, Achilles tendon insertion, left and right) (Healy and Helliwell 2008). Each site is assigned a score of 0 (absent) or 1 (present); the results from each site are then added to produce a total score (range 0 to 6).

9.1.2.10. Spondyloarthritis Research Consortium of Canada

If the patient has enthesitis, the SPARCC will be administered by a blinded assessor. The SPARCC enthesitis index evaluates tenderness in a total of 16 enthesitis sites: the greater trochanter (right/left [R/L]), quadriceps tendon insertion into the patella (R/L), patellar ligament insertion into the patella and tibial tuberosity (R/L), Achilles tendon insertion (R/L), plantar fascia insertion (R/L), medial and lateral epicondyles (R/L), and the supraspinatus insertion (R/L) (Mease 2011). Tenderness at each site is quantified on a dichotomous basis: 0 = nontender and 1 = tender. The results from each site are then added to produce a total score (range 0 to 16).

